5.4 Treatment blinding

This is a double-blind randomized treatment trial. Unblinding will occur after Week 16 database lock to support regulatory submission. However, subjects, investigators, site personnel and persons performing the assessments will remain blinded to original treatment assignment from the time of randomization until the final database lock and analyses are completed, using the following methods: (1) Randomization data are kept strictly confidential until the time of unblinding and will not be accessible by anyone else involved in the study with the following exception: bioanalyst; (2) The identity of the original randomized treatments administered through Week 16 will be concealed up to the final database lock and analyses are completed by the use of study treatments in the form of PFS for s.c. injection, filled with secukinumab or placebo, that are identical in appearance, during the double-blind treatment period.

Other unblinding of treatment dose or original randomized treatment assignment before the final database lock and analyses are completed will only occur in the case of patient emergencies (see [Section 5.5.12](#)).

The randomization codes associated with patients from whom [REDACTED] samples are taken will be disclosed to the bioanalyst who will keep [REDACTED] results confidential until database lock. The bioanalyst will have access to the randomization list to facilitate analysis of the [REDACTED] [REDACTED] samples (i.e., to avoid the unnecessary analysis of placebo samples). Whenever needed or requested by the clinical team, the bioanalyst will share information from [REDACTED] measurements before clinical database lock in a blinded fashion [REDACTED].

The hsCRP results from samples collected during the treatment period will be revealed only after the database lock and analyses are completed.

5.5 Treating the patient

5.5.1 Patient numbering

Each subject is uniquely identified by a Subject Number which is composed by the site number assigned by Novartis and a sequential number assigned by the investigator. Once assigned to a subject, the Subject Number will not be reused.

Upon signing the informed consent form, the subject is assigned the next sequential number by the investigator. The investigator or his/her staff will contact the IRT and provide the requested identifying information for the subject to register them in the IRT. The site should select the electronic case report form (eCRF) book with a matching Subject Number from the electronic data capture (EDC) system to enter data.

If the subject fails to be treated for any reason, the IRT must be notified within 2 days that the subject was not treated. The reason for not being treated will be entered on the Screening Phase Disposition eCRF page.

Subjects may be re-screened once and will receive a new Subject Number after they have been re-consented. Subjects who are mis-randomized cannot be re-screened; mis-randomization occurs when a subject who does not meet all eligibility criteria receives a randomization number in error.

5.5.2 Dispensing the investigational treatment

Each study site will be supplied by Novartis with investigational treatment (150 mg secukinumab vs placebo) in packaging of identical appearance.

The investigational treatment packaging for secukinumab/placebo has a 2-part label. A unique medication number is printed on each part of this label, which corresponds to placebo or active treatment. Investigator staff will identify the investigational treatment packages to dispense to the subject by contacting the IRT and obtaining the medication numbers. Immediately before dispensing the package to the subject, investigator staff will detach the outer part of the label from the packaging and affix it to the respective source document (Drug Label Form) for the subject.

5.5.3 Handling of study treatment

Investigational treatment must be received by a designated person at the study site, handled and stored safely and properly, and kept in a secured location to which only the investigator and designees have access. Upon receipt, all investigational treatment should be stored according to the instructions specified on the labels. Clinical supplies are to be dispensed only in accordance with the protocol.

Medication labels will be in the local language and comply with the legal requirements of each country. They will include storage conditions for the investigational treatment but no information about the subject except for the medication number.

The PFS (150 mg active/placebo) sealed in an outer box must be stored in a access controlled/locked refrigerator between 2°C and 8°C (36°F and 46°F) and protected from light and should not be frozen. They must be carefully controlled in accordance with regulations governing investigational medicinal products and local regulations.

The investigator must maintain an accurate record of the shipment and dispensing of investigational treatment in a Drug Accountability Log. Monitoring of drug accountability will be performed by the field monitor during site visits and at the completion of the trial.

At the conclusion of the study, and as appropriate during the course of the study, the investigator will return all partly used and unused investigational treatment (including placebo), packaging, drug labels, and a copy of the completed Drug Accountability log to Novartis as instructed.

Destruction of the unused drug should be done according to local requirements and after approval by Novartis clinical team.

5.5.4 Instructions for prescribing and taking study treatment

All study treatment (150 mg secukinumab/placebo) will be self-administered by the subject subcutaneously throughout the study, at the study site, after the study assessments for the visit have been completed. Site staff will administer the injection only to those subjects who feel insecure to self-administer the PFS injection.

Detailed instructions for self-administration of the study treatment will be given in the instructions for use (IFU) provided to each subject. Self-injection will take place under the supervision of a site staff member. At the randomization visit, the subject will be instructed by the site staff, utilizing the IFU on how to self-inject via prefilled syringes. Subjects will be asked to raise questions, if they have any, and then to proceed with self-injection of the study drug.

The first study treatment administration will occur at the randomization visit after the inclusion/exclusion criteria have been confirmed, all study scheduled assessments have been performed and the scheduled blood samples have been drawn.

At study visits when pre-dose blood has to be drawn ([Table 6-1](#)), the subject will self-inject the study treatment only after blood samples have been taken. All dates and times of injections self-administered by the subject during the study must be recorded in the Dosage Administration Record eCRF. Immediately before dispensing the package to the subject, investigator staff will detach the outer part of the label from the packaging and affix it to that subject's source document (Drug Label Form).

Once the s.c. injection has been completed and the condition of the subject is deemed stable by the investigator or designated healthcare professional, the subject can be discharged

The investigator should promote compliance by instructing the patient to attend the study visits as scheduled and by stating that compliance is necessary for the patient's safety and the validity of the study. The patient should be instructed to contact the investigator if he/she is unable for

any reason to attend a study visit as scheduled or if he/she is unable for any reason to take the study treatment as prescribed.

5.5.5 Permitted dose adjustments and interruptions of study treatment

Study treatment dose adjustments are not permitted. Study treatment interruption is also not permitted with the following exceptions:

Study treatment interruption is only permitted if, in the opinion of the investigator, a subject is deemed to be placed at a significant safety risk unless dosing is temporarily interrupted. In such cases study treatment should be interrupted only during the time that this risk is present and ongoing. Study treatment can be restarted at the next scheduled visit after resolution of the safety risk.

The effect of secukinumab on live vaccines is unknown; therefore, live vaccines should not be administered during participation in the study. In case a live vaccine has been administered due to a medical urgency, study treatment should be interrupted for 12 weeks.

Any study treatment interruption must be recorded on the Dosage Administration Record eCRF.

5.5.6 Escape medication

Escape medication is defined as any new therapeutic intervention or a significant change to ongoing therapy made because a subject is experiencing either no benefit from participation in the trial or worsening/exacerbation of their disease. Escape medication must not be used before completion of Week 20 assessments. Although no subject will be restricted from receiving necessary escape medications for lack of benefit or worsening of disease, if escape with prohibited biologics (as described in [Section 5.5.8](#)) occurs, subjects will be discontinued from the study and enter into the follow-up period after an end of study visit. Efficacy will be assessed in detail at every study visit, and subjects who are deemed not to be benefiting from the study treatment based on safety and efficacy assessments by the investigator or for any reason on their own accord will be free to discontinue participation in the study at any time. Changes in NSAID concomitant therapy are permitted after Week 20 assessments as per investigator's clinical judgment. Please see [Section 5.5.7](#) and [Section 5.5.8](#) for details.

Any use of escape medication must be recorded in the Prior/Concomitant medications eCRF.

5.5.7 Concomitant treatment

The investigator should instruct the subject to notify the study site about any new medications (including over-the-counter drugs, traditional Chinese medicine, calcium and vitamins) administered after the subject was enrolled into the study. All medications (other than study treatment), procedures and significant non-drug therapies (including physical therapy and blood transfusions) must be recorded on the Prior and Concomitant medications or Procedures and Significant Non Drug Therapy eCRF. The reason, name of the drug, procedure or non-drug therapy should be listed.

Guidelines for the use of specific medications are provided below:

Methotrexate

Subjects taking MTX (up to 25 mg/week) must be on a stable dose for at least 4 weeks before randomization and maintained stable until Week 52, except if MTX-related adverse events develop.

Folic acid

Subjects on MTX must be taking folic acid supplementation before randomization and during the trial to minimize the likelihood of MTX-associated toxicity.

Leflunomide wash-out with cholestyramine

In case of leflunomide treatment, a drug wash-out of 8 weeks has to be performed. However, another wash-out procedure might be considered. Cholestyramine can be given orally to wash-out the drug at a dose of 8 g t.i.d. Cholestyramine reduced plasma levels of the active leflunomide metabolite by approximately 40% in 24 hours and by 49% to 65% in 48 hours in three healthy volunteers. The administration of cholestyramine is recommended in subjects who require a drug elimination procedure. A subject who has received 8 g t.i.d. for 11 days can be safely randomized 4 weeks after the beginning of the 11-day treatment period.

Systemic corticosteroids

Treatment with systemic corticosteroids is permitted up to a maximum daily dose of 10 mg prednisone equivalent and if the dose was stable within the 2 weeks preceding randomization.

Corticosteroid dose reductions below 10 mg prednisone equivalent are permitted after Week 20, although the corticosteroid dose should not be reduced by more than 1 mg prednisone equivalent every 4 weeks.

Intra-articular corticosteroids are not permitted within the 4 weeks preceding randomization and up to Week 20. After Week 20, no more than 1 joint per 24-week period may be injected. No single injection should exceed 40 mg of triamcinolone (or equivalent) and the total dose of intra-articular corticosteroid may not exceed 80 mg of triamcinolone (or equivalent) during any 52-week period. Injection of intra-articular steroids is not permitted within 8 weeks prior to Week 52.

Any change in the dose of systemic corticosteroids, or any corticosteroid injections, during the trial must be recorded on the corresponding eCRF page.

Non-steroidal anti-inflammatory drugs (NSAIDs) (including COX-1 or COX-2 inhibitors), low strength opioids and acetaminophen/paracetamol

Subjects regularly using NSAIDs, low strength opioids, or paracetamol/acetaminophen should be on stable dose for at least 2 weeks before randomization to allow inclusion. They should remain on a stable dose in the study up to Week 20.

Subjects taking NSAIDs, low strength opioids or paracetamol/acetaminophen PRN within the 2 weeks before randomization can continue to do so in the study; however, they have to refrain from any intake during at least 24 hours before a visit with disease activity assessment.

After Week 20 assessments are completed, a change in the NSAIDs, low strength opioids, or paracetamol/acetaminophen treatment regimen is permitted

Any change of the NSAIDs, low strength opioids, or paracetamol/acetaminophen treatment during the trial should be recorded on the appropriate prior and concomitant medication eCRF page.

5.5.8 Prohibited Treatment

Table 5-1 Prohibited treatment

Prohibited treatments	Washout period (before randomization)
Etanercept*	4 weeks
Infliximab*	8 weeks
Adalimumab, golimumab, certolizumab*	10 weeks
Unstable dose of MTX or sulfasalazine	4 weeks
Other DMARD (except MTX or sulfasalazine)	4 weeks
Leflunomide	8 weeks
Leflunomide with Cholestyramine washout	4 weeks
Unstable dose of NSAIDs (COX1 or COX2 inhibitors) (until Week 20)	2 weeks
Systemic corticosteroids > 10 mg prednisone equivalent**	2 weeks
Intra-articular steroids injections (until Week 20)	4 weeks
Any biological immunomodulating agents, except those targeting TNF α *	No prior exposure
Any cell-depleting therapies including but not limited to anti-CD20 or investigational agents (e.g., CAMPATH, anti-CD4, anti-CD5, anti-CD3, anti-CD19)	No prior exposure
Any investigational treatment or participation in any interventional trial	4 weeks or 5 half-lives (whichever is longer)
Analgesics other than paracetamol/acetaminophen or low strength opioids PRN	4 weeks
Live vaccinations	6 weeks

* These agents fall under the category of biologic immunomodulators and are prohibited medications. Administration of these agents requires study discontinuation (see [Section 5.5.8](#)).

** See details about corticosteroid management in [Section 5.5.7](#).

5.5.9 Discontinuation of study treatment and premature withdrawal

Subjects may voluntarily discontinue from the study for any reason at any time. They may be considered discontinued if they state an intention to withdraw, fail to return for visits, or become lost to follow-up for any other reason.

If premature discontinuation occurs for any reason, the investigator must make every effort to determine the primary reason for a subject's premature discontinuation from the study and record this information on the appropriate Study Phase Completion eCRF.

Patients who discontinue study should undergo an end of treatment visit (Week 52) at 4 weeks after last study treatment and then also return after an additional 8 weeks for a final follow-up visit, corresponding to Week F60 (12 weeks after last study treatment; see [Table 6-1](#)). The final follow-up visit should be performed before any new treatment is initiated. Study treatment discontinuation must also be recorded in IRT.

Subjects who are prematurely withdrawn from the study will not be replaced.

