3.1 Study design

This multicenter study uses a randomized, double-blind, placebo-controlled, parallel-group design. A screening (SCR) period running up to 10 weeks before randomization will be used to assess eligibility, followed by 52 weeks of treatment.

[figure not shown]
At baseline, patients will be randomized to one of the two treatment groups:

- **Group 1: 300 patients**, secukinumab 150 mg (1 mL, 150 mg/mL) s.c. PFS at BSL, Weeks 1, 2, and 3, followed by administration every four weeks starting at Week 4
- **Group 2: 150 patients**, placebo (1 mL) s.c. PFS at BSL, Weeks 1, 2, 3, 4, 8, and 12, followed by secukinumab 150 mg (1 mL, 150 mg/mL) administration every four weeks starting at Week 16

The patients will be stratified at randomization according to the region (China and non-China). Approximately 80% of randomized patients will be from China (360 Chinese patients) in order to evaluate the efficacy and safety in this patient population. No more than 30% TNF α Inhibitor Incomplete Responders (TNF-IR) patients will be enrolled in the study.

Starting at Week 16, all patients will switch to open-label secukinumab 150 mg, including all placebo patients; however, all patients and investigators/site staff will remain blinded to the original randomized treatment group assignment (150 mg vs placebo). Study treatment will continue up to Week 48.

An end of treatment visit is to be done 4 weeks after last study treatment administration and a post treatment follow-up visit is to be done 12 weeks after last study treatment administration for all subjects (regardless of whether they complete the entire study as planned or discontinue prematurely).

Figure 3-1 **Study design**

Subjects will be instructed in detail how to self-administer the s.c. injection using PFS. Each injection will be administered into an appropriate injection site of the body (thighs, arms, or abdomen). All injections will be performed at the study site. Site personnel may administer the injections to subjects who are not able to, or feel insecure to self-administer (see [Section 5.5.4](#) for more details).

Rescue medication is not allowed until Week 20 (see [Section 5.5.6](#) for more details). However, subjects who are deemed by the investigator not to be benefiting from the study treatment based on safety and efficacy assessments or for any reason of their own accord will be free to discontinue participation in the study at any time.

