5.5.13 Study completion and post-study treatment

A subject will be considered to have completed the study if he/she received a maximum of 52 weeks of study treatment and upon completion of the scheduled study assessments and procedures up to and including Visit F60.

Information on the subject's completion or discontinuation of the study and the reason for discontinuation will be recorded on the appropriate Study Phase Completion eCRF page.

The investigator must provide follow-up medical care for all subjects who are prematurely withdrawn from the study, or must refer them for appropriate ongoing medical care. This medical care may include initiating another treatment outside of the study as deemed appropriate by the investigator. This treatment may be any non-biologic DMARD. In case of a biologic treatment, a waiting period of 3 months before initiating the treatment is recommended.

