13.1 Adverse events

The crude incidence of treatment emergent adverse events (i.e. events started after the first dose of study treatment or events present prior to the first dose of study treatment but increased in severity based on preferred term and on or before last dose date + 84 days) will be summarized

by primary system organ class and preferred term. Confidence intervals for the crude rate will be derived as described in [Section 16.2.4.1](#). In addition, exposure time-adjusted incidence rates including 95% confidence intervals will be provided for the entire treatment period (see [Section 16.2.5.1](#)). A graphical display of the crude incidence rates and exposure-adjusted rates will be presented for all AEs and serious AEs by system organ class.

Adverse events reported will be presented in descending frequency according to its incidence in the secukinumab group starting from the most common event. Summaries (crude incidences only) will also be presented for AEs by severity and for study treatment related AEs. If a particular AE 'severity' is missing, this variable will be listed as missing and treated as missing in summaries. If a subject reported more than one adverse event with the same preferred term, the adverse event with the greatest severity will be presented. If a subject reported more than one adverse event within the same primary system organ class, the subject will be counted only once with the greatest severity at the system organ class level, where applicable.

Separate summaries will be provided for adverse events suspected to be related to study drug, deaths, serious adverse events, and adverse events leading to discontinuation and adverse events requiring concomitant medication.

Separate summaries will be provided for SAEs and significant AEs that led to treatment discontinuation or dose adjustment or interruption by site in China.

Adverse events will also be reported separately by SMQ according to MedDRA, using a narrow search. The MedDRA version used for reporting the study will be described in a footnote.

A listing of non-treatment emergent adverse events will be provided. These adverse events occurred before the first dose of the study treatment. The crude incidence rate will be provided without treatment information.

For SAEs occurred during screening a listing will be prepared for all subjects screened including screening failures.

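### Protocol 5.5.6, 5.5.9 and 5.5.13 do not give one rule on new therapy before the F60 visit, and the SAP does not identify treatment-emergent events that start after such therapy

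*Protocol*

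**What the plan says.** Three sections of the Protocol deal with therapy after a patient leaves study drug.

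- **5.5.9.** Patients who discontinue have an end-of-treatment visit 4 weeks after the last dose and F60 a further 8 weeks later. Then: "The final follow-up visit should be performed before any new treatment is initiated". No drug class is excepted. Section 3.1 gives the same timing for everyone: "a post treatment follow-up visit is to be done 12 weeks after last study treatment administration for all subjects".
- **5.5.13.** For prematurely withdrawn patients: "This medical care may include initiating another treatment outside of the study as deemed appropriate by the investigator". It continues: "This treatment may be any non-biologic DMARD". For biologics it says: "In case of a biologic treatment, a waiting period of 3 months before initiating the treatment is recommended". None of these sentences refers to F60, and the point from which the 3 months run is not given.
- **5.5.6.** Escape medication is barred until the Week 20 assessments are done. If a patient escapes with a prohibited biologic, "subjects will be discontinued from the study and enter into the follow-up period after an end of study visit".

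SAP 13.1 counts an adverse event as treatment-emergent if it starts or worsens after the first dose and "on or before last dose date + 84 days". SAP 13.2 to 13.4 apply the same limit to laboratory data, vital signs and ECG. SAP section 10 treats medication taken up to 84 days after the last dose as concomitant and tabulates it by treatment group. Nothing in the SAP marks or separates events that begin after a new AS therapy.

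**The concern.** The three sections answer one practical question differently: may a patient who has stopped study drug start other AS therapy before F60? Section 5.5.9 says the visit comes first. Section 5.5.13 permits a non-biologic DMARD without reference to the visit. Section 5.5.6 describes a patient for whom a biologic has already come first. The question will arise in practice, because 5.5.9.1 tells investigators to stop study treatment for lack of improvement or worsening.

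Two things are at stake. Sites have no single instruction for these patients. And the late safety data may carry the effects of another drug while being counted under the trial treatment received.

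**Working it through.** **1. Do the visit and the analysis window coincide?** Inputs: last scheduled dose at Week 48, end-of-treatment visit 4 weeks later and follow-up 12 weeks later (Protocol 3.1); AE limit of last dose + 84 days (SAP 13.1).

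- 48 + 4 = Week 52 and 48 + 12 = Week 60, as the schedule states.
- 12 × 7 = 84 days, as the SAP states.

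So any therapy started before a 12-week F60 visit starts inside the treatment-emergent window.

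**2. The rules in pairs.**

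| Pair | Situation | Result |
|---|---|---|
| 5.5.9 and 5.5.13 | Non-biologic DMARD | Conflict if the permission is used before F60: visit first (84 days) against no stated wait. None if the site waits. |
| 5.5.9 and 5.5.13 | Biologic after withdrawal | Three calendar months are 89 to 92 days, longer than 84. Compatible if counted from the last dose. |
| 5.5.9 and 5.5.6 | Escape with a prohibited biologic | Conflict: the biologic is taken before follow-up begins, so F60 cannot precede it. |
| 5.5.13 and 5.5.6 | Escape with a prohibited biologic | The recommended wait has already been passed over. |

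**3. Share of the window affected.** If new therapy starts s days after the last dose, the share is (84 − s)/84. The values of s are assumptions; the documents give none.

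- s = 28: 56/84 = 67%
- s = 42: 42/84 = 50%
- s = 56: 28/84 = 33%

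**4. Scale across the trial.** Protocol section 4 anticipates 10% drop-out at the primary endpoint: 0.10 × 450 = 45 patients. Suppose, as an extreme, that all 45 start new therapy.

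- From day 28: 45 × 56/365.25 = 6.9 patient-years.
- From day 0: 45 × 84/365.25 = 10.3 patient-years, which is their whole post-treatment window.
- For comparison, the other 405 patients followed for 60 weeks give 405 × 420/365.25 = 465.7 patient-years. The ratios are 6.9/465.7 = 1.5% and 10.3/465.7 = 2.2%.

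These ratios are rough. The denominator omits the drop-outs' own time and assumes no later withdrawals, and later withdrawals would add to the numerator.

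**The case against.** The strongest reply is that 5.5.13 permits and does not require. A site that holds F60 at 12 weeks and starts a DMARD afterwards complies with both 5.5.9 and 5.5.13, and 5.5.13 can be read as naming suitable drugs without overriding the visit order. That stands. A reader might infer that no site can follow the text; this is true only of biologic escape. It does not remove the mismatch, because a site that uses the permission as written departs from 5.5.9 and nothing in 5.5.13 says so.

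Three other stronger readings are tempting and not supported.

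- **That the safety window is cut short.** No passage lets F60 move forward. The 12-week timing is the same in 3.1, 5.5.9, section 6 and the footnote to Table 6-1, and SAE reporting runs for at least 12 weeks after the last dose (7.2).
- **That placebo results will absorb events from other biologics.** Escape is barred before Week 20, and placebo patients move to secukinumab at Week 16. A biologic soon after early withdrawal would also depart from 5.5.9 and from the 5.5.13 recommendation. What the text does allow is a non-biologic DMARD in a withdrawn placebo patient, whose events would be counted under placebo.
- **That sites do handle patients differently.** This is foreseeable, but the documents do not report it.

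It is also fair to say that the SAP is not blind to other therapy. It tabulates concomitant medication over the same 84 days and summarises study-drug-related AEs, and the AE record captures other medication taken (Protocol 7.1). Counting every event in a fixed post-dose window is a legitimate main analysis. None of this shows which events followed the start of a new AS therapy.

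**Conclusion.** The inconsistency is real and no other section resolves it. It is confined to two situations: a withdrawn patient who starts a non-biologic DMARD before F60, and a patient who escapes with a prohibited biologic. The biologic wait in 5.5.13 is not a conflict with 5.5.9, provided it runs from the last dose.

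The consequence falls on post-treatment safety data. The number affected cannot be derived from the documents. The 45 expected drop-outs are a loose ceiling for the period to Week 16: patients who withdraw consent have no further assessments (Protocol 5.5.10), some will be lost to follow-up, and others will start nothing new. Later withdrawals add an unknown number. The effect on total exposure is likely to be small, although for an affected patient a third to two thirds of the window could be involved under the assumed start times.

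The primary ASAS20 comparison is largely protected, because patients who drop out count as non-responders through Week 16 whatever they take next (SAP 11.3). The point should be corrected, but it does not threaten the main result.

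**What to change.** **Protocol.** The sponsor must reconcile 5.5.6, 5.5.9 and 5.5.13 so that all three state the same rule on new therapy before F60, separately for biologic and non-biologic drugs, and say from when any waiting period runs. No clinical rule is proposed here.

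**SAP.** In section 13, flag treatment-emergent events and laboratory values that start after the first dose of any new AS therapy. The flag should cover DMARDs as well as biologics, since the mismatch between 5.5.9 and 5.5.13 concerns DMARDs. Keep the fixed 84-day window as the main analysis, and show the main AE table with and without flagged events as a supportive display.

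**Cost.** Wording at the next amendment, one derived flag and one extra AE table. No new data collection is needed: Protocol 5.5.6 and 5.5.7 already require escape and other new medication to be recorded on the eCRF, and SAP section 10 already works with recorded or imputed start dates. The flag will be incomplete for patients who do not return for follow-up.
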